- Aim 2: Develop an evidence-based intervention to reduce head impact exposure in youth football practices, using a community-engaged approach.
- *Aim 3:* Pilot-test the evidence-based practice structure to reduce head impact exposure and mitigate changes in clinical outcomes in youth football.

We **hypothesize** that (a) determinants at the individual (athlete), interpersonal (team & coach), and community levels (built & social environment) of the social ecological model⁸⁴ may be identified and targeted to reduce head impact exposure in youth football practices, and (b) an evidence-based strategy to reduce head impact exposure in practices may be developed and pilot tested using a community-engaged approach. (c) The reduction in exposure will be associated with a lower rate of change in pre- to post-season clinical outcome measures and cognitive function scores.

Methods and Measures

Design

Two local youth football teams at the middle school level (ages 11-14) will be recruited to participate in this study. Informed consent and signed assent forms will be obtained from parents/legal guardians of participating youth football players. All interested football players on the 2 teams will be enrolled; of those enrolled, 15-20 per team (n=30-40 total) will be randomly selected for instrumentation with head impact sensors using a random numbers table. Head impact sensors embedded in a custom mouthpiece will be used to collect head impact exposure in conjunction with on-field video data for a season. These data will be used to inform guided discussions with stakeholders (parents, coaches, league officials). Using an audit and feedback approach (sharing biomechanical data with the stakeholders), we will facilitate semi-structured focus groups with the coaches (n=8) and parents (n=10) of the participating teams, and key informant interviews with league officials (n=8), to assess the awareness and receptivity to creating a safer practice structure. Participants will be asked to complete a series of cognitive, vestibular/ocular motor, and postural stability tasks pre- and post-season.

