All parents with athletes participating on the prospective teams and coaches of the prospective teams will be eligible for participation in the study. All league officials of the governing organization will be eligible for participation in the study.

Surveys:

All parents, coaches, and league officials of the governing youth football organization will be eligible for participation in the survey portion of the study.

Exclusion Criteria

Mouthpiece and Clinical Outcome Data Collection:

Athletes will be excluded from participation if they have had braces less than 6 months, or have dental appliances that may impede the fit of the mouthpiece device (e.g., Herbst Appliance).

Sample Size

Study Sample - Athletes: Each year of the study, we will identify two middle school (ages 11-14) football teams for this study. All interested athletes on these teams will be invited to voluntarily participate in biomechanical data collection; of those enrolled, 15-20 per team will be randomly selected for instrumentation with head impact sensors. Informed consent will be obtained from parents/legal guardians of all athletes; participating athletes will sign assent forms. The number of athletes (N=30-40 each year, N=105-130 total) was chosen based on our earlier studies, which reported significant differences in exposures among football conditions with sample sizes of 9^{85} , 40^{86} and 30^{87} . We aim to accrue sufficient information to assess relationships (e.g. between measures of exposures) and describe variability among exposure levels among conditions and athletes. N=30 provides >80% power to detect correlations of r>=0.50, i.e. associations of sufficient strength to inform design of the intervention (Aim 3). It also provides sufficient precision for estimating standard deviations: 90% confidence intervals will range from 0.83 to 1.28 SD units. Additionally, a Fall 2022 football cohort (N=14) from Head Kinematics in Sports Study (IRB00049715) will be included in biomechanics data collection and analysis. In Fall 2024, we plan to enroll (n=55) athletes across two of six participating teams to participate in parallel biomechanical and video data collection to evaluate the frequency and severity of head impacts experienced throughout the season.

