Triggers refer to the standards an athletic trainer or coach will use to determine whether or not an impacted player should receive further testing. The triggers for testing will be the standard already used by the athletic trainers and will not be altered due to this study. If a concussion is suspected, the athletic trainers typically use the SCAT5 on-field to determine whether to remove an athlete from play. Following removal from play, the athletic trainers use the SCAT5 to assist with a clinical diagnosis of concussion which would trigger further testing. Athletic trainers and physicians will follow normal methods for diagnosis and treatment of a concussion and not be restricted to only the information found in this protocol.

Post-Injury Testing:

Post-injury testing is any testing that is administered after a player has been diagnosed by a team physician or athletic trainer to have a concussion. The records for Post-Injury Testing will only be provided and used for research analysis AFTER a concussion has been diagnosed, pending signed authorization by the players on the Informed Consent document. No additional or different testing will be done because of a player's participation in the study.

Post-injury testing will include baseline cognitive, postural control, and vestibular/ocular motor testing within 24-48 hours after concussion diagnosis.

Outcome Measure(s)

- Primary Outcomes:
 - o Number of head impacts, impact rate
 - Mean and 95th percentile number of impacts, linear acceleration, rotational acceleration by session type, activity, skill and behavior
 - Pre- to Post-Season change scores for:
 - ImPACT
 - NIH Toolbox
 - RAVLT
 - Postural Control
 - VOMS
 - Conners' CPT
- Secondary Outcomes:
 - Implementation facilitators and barriers
 - Intervention fidelity
 - Adaptation of the intervention

Analytical Plan

Statistical analysis of biomechanical data will be based on our previous approaches.^{9,11,64} Head impact data will be transformed to the head center of gravity using Matlab (Mathworks, Inc., Natick, MA) and quantified for each session (i.e., practice or game) and practice drill category (i.e., conditioning, tackling) and across drill types (i.e., Oklahoma, one-on-one) in terms of mean number of impacts and impact rate and mean and 95th percentile head acceleration.

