On-field head impact data for each athlete will be quantified for each practice or game by number of impacts, impact rate, mean, median, and 95th percentile of head acceleration, and location of impact. Impact rates and percentiles (i.e., 50th, 95th) computed from the distribution of accelerations will be compared between unexposed (year 2, published iTAKL and BRP study data^{61,106–108}) and exposed seasons of data collection. Mixed-effects models (in SAS) will be used to assess differences in head impact exposure in practices and games before (year 2, published iTAKL and BRP study data^{61,106–108}) and after the intervention, adjusting for confounding factors, including team. We will examine the consistency of intervention effects on exposure outcomes between teams and among players over time, with the goal of learning how to refine and tailor the intervention to increase adherence and potential effectiveness. Because this is a pilot study, we will lack sufficient power to fully test the effectiveness of the intervention; however, we will gather essential information for a future R01-supported randomized control trial.

All clinical assessment scores will be compared to same age peers at testing time (via published normative values) to control for developmental changes that may occur during the study period. Scores will be normalized (i.e. z-scores) to facilitate comparisons among cognitive tests. Kinematic metrics (i.e., total impacts, 95th percentile accelerations and rotational velocity, RWE) will be time-varying covariates in generalized linear and mixed effects models. The modeling framework, with its random effects structure, will allow for assessment of clinical outcome differences pre- to post-season over time between the intervention athletes and controls. We will also describe whether associations may vary according to athletes' characteristics.

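### The clinical change-score analysis names no use of the pre-season score, which may cost precision in the exposure association; the model should be written out and should use that score

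*Combined protocol and SAP*

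**What the plan says.** Outcome Measure(s) lists among the primary outcomes "Pre- to Post-Season change scores for" six instruments: ImPACT, NIH Toolbox, RAVLT, postural control, VOMS and Conners' CPT. Hypothesis (c), under Objectives, depends on them: "The reduction in exposure will be associated with a lower rate of change in pre- to post-season clinical outcome measures".

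The Analytical Plan sets the scale of the scores. "All clinical assessment scores will be compared to same age peers at testing time (via published normative values) to control for developmental changes", and "Scores will be normalized (i.e. z-scores) to facilitate comparisons among cognitive tests". It then says that kinematic metrics "will be time-varying covariates in generalized linear and mixed effects models", and that these models, through their random effects, "will allow for assessment of clinical outcome differences pre- to post-season over time between the intervention athletes and controls".

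No pre-season clinical score is named as a covariate. Adjustment for confounders, including team, is written for the head impact exposure models only. The fixed effects, the covariance structure and the contrast of the clinical models are not written out.

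The only power figure is under Sample Size: "N=30 provides >80% power to detect correlations of r>=0.50". It is offered for associations that would inform the design of the intervention, not for the clinical outcomes.

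**The concern.** A change score fixes the slope of post-season on pre-season at 1. When the pre-post correlation is below 1 and the two visits have similar spread, that slope is too steep, and the change carries the measurement noise of both tests. Regressing the post-season score on the pre-season score estimates the slope and removes the excess noise. The season's head impacts come after the pre-season test, so that score is a pre-exposure covariate. A change score already requires it, so adjustment needs no extra data.

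Norming does not do this job. It removes the expected effect of age, but it does not use the athlete's own starting level to reduce residual variance.

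With 30 to 40 athletes a season, precision is scarce. The plan also intends the pilot to inform a later randomised trial, for which residual variances and adjusted estimates would be useful planning inputs.

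**Working it through.** **1. The plan's own figure.** Inputs from Sample Size: N=30, r=0.50. No alpha is stated; two-sided 0.05 is assumed. Fisher z: atanh(0.50) × √27 − 1.96 = 0.549 × 5.196 − 1.96 = 0.894, which gives power of 81.4%. A simulated t-test for r gives 82.7%. The statement of more than 80% reproduces.

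**2. Variance ratio.** Assume equal SDs of 1 at both visits and a pre-post correlation rho.
- Change score: Var = 2(1−rho).
- Post-season score given pre-season score: Var = 1−rho².
- Ratio, adjusted to change: (1+rho)/2.

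**3. Illustration for the exposure association.** Take r=0.50 as the correlation between exposure and change, and assume exposure is unrelated to the pre-season score. Exposure then explains 0.25 of Var(change), so its partial correlation after adjustment is √(0.25/ratio). Power is Φ(atanh(partial r) × √26 − 1.96), with one degree of freedom spent on the covariate.

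| rho (assumed) | Variance ratio | Partial r | Power, adjusted | Power, change |
|---|---|---|---|---|
| 0.5 | 0.75 | 0.577 | 91.9% | 81.4% |
| 0.6 | 0.80 | 0.559 | 89.6% | 81.4% |
| 0.7 | 0.85 | 0.542 | 87.2% | 81.4% |
| 0.8 | 0.90 | 0.527 | 84.8% | 81.4% |
| 0.9 | 0.95 | 0.513 | 82.4% | 81.4% |

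At rho 0.5 the gain is worth 30/0.75 = 40 athletes instead of 30.

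**4. Does the mixed model already recover this?** It depends on how the model is written.
- *Group-by-time.* In a simulated complete two-visit data set, a random-intercept model with group, time and their interaction gave 0.243 (SE 0.177). The plain difference in mean change was also 0.243 (SE 0.177). Nothing is gained from baseline.
- *Exposure as a time-varying covariate*, coded 0 pre-season and x post-season, with no exposure main effect. This constrains the expected pre-season score to be equal at all exposure levels. Simulated power at N=30 for change / adjusted / this model was 83% / 93% / 92% at rho 0.5, 84% / 90% / 89% at 0.7 and 84% / 87% / 87% at 0.8. The gain is recovered.

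**5. Group contrast.** Assumptions: 30 athletes per group, a difference of 0.5 SD, two-sided 0.05, team clustering ignored. Power for change against adjusted is 49% against 61% at rho 0.5, 71% against 77% at 0.7, and 99.1% against 99.3% at 0.9.

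If the groups differ at baseline by D, the two estimates differ by (1−rho) × D. For D = 0.5 SD that is 0.25 SD at rho 0.5, 0.15 at 0.7 and 0.05 at 0.9.

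**The case against.** The strongest objection is that the plan calls the kinematic metrics time-varying covariates. Season impacts are naturally zero at the pre-season test, and step 4 shows that this coding, without an exposure main effect, already recovers the precision. That is right as far as it goes. However, the plan states neither the pre-season coding nor the absence of a main effect, and a 95th-percentile acceleration has no natural pre-season value. The objection therefore shows that the loss is conditional on how the model is written; it does not show that the plan avoids it.

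A second objection concerns the intervention contrast. Intervention teams are recruited as a new set and are not randomised. If teams differ stably before the season, the change score is unbiased and the adjusted estimate is off by (1−rho) × D. This stands. Making the adjusted model the main one for that contrast would be a judgement call.

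Third, the consequence is limited. The r=0.50 case was not written for the clinical outcomes, the plan says the pilot lacks power to test effectiveness fully, and the gain is only 1 to 3 points at rho 0.9 to 0.8. This also stands.

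Three stronger readings are tempting, but the documents do not support them:
- *That the change scores are raw.* They are age-normed and converted to z-scores.
- *That regression to the mean biases the results.* Athletes are not selected on pre-season scores. With 30 per group, a one-standard-error chance imbalance of √(2/30) = 0.26 SD shifts the change contrast by (1−rho) × 0.26, or 0.13 SD at rho 0.5. That averages to zero and is already in the standard error.
- *That every tested athlete supplies a baseline on every instrument.* Under Neurocognitive Assessments the testing is optional, and ImPACT is described only after a concussion diagnosis.

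**Conclusion.** The point holds as a matter of precision and specification. As written, the plan names no use of the pre-season score. If the clinical outcomes are analysed as change scores, or by a two-visit random-intercept group-by-time contrast, residual variance is higher than it need be: the adjusted variance would be 25%, 15% or 5% lower at rho 0.5, 0.7 or 0.9. In the borrowed N=30, r=0.50 illustration, that is about 11, 6 or 1 points of power.

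These figures rest on assumed values of rho, equal SDs at both visits, exposure unrelated to the pre-season score, and no team clustering. They do not apply if exposure is coded zero pre-season with no main effect.

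Explicit adjustment is justified for the exposure association. For the non-randomised group contrast, only side-by-side reporting is.

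**What to change.** 1. **Exposure association.** For each instrument with a pre-season test, state the model as post-season z-score on pre-season z-score plus the season exposure metric, with the planned team and athlete structure. The equivalent constrained-baseline mixed model would also serve, provided the pre-season coding of exposure and the absence of an exposure main effect are written down.
2. **Intervention against control.** Report the baseline-adjusted and change-score estimates side by side. Base no conclusion on either alone, and say that they differ by (1−rho) times any stable baseline difference.
3. **ImPACT.** Leave it out of both analyses until its listing as a change score under Outcome Measure(s) is reconciled with Neurocognitive Assessments, which describes it only after a concussion diagnosis.

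For the other instruments the cost is analysis-plan wording and one degree of freedom per model, with no new data. The downside is two estimates to interpret for the group contrast.

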Appendix 1. Timeline

Appendix 2. Stakeholder Surveys

Youth Football Stakeholder Survey

We would like to invite you to take part in a research project. The purpose of this research is to understand the knowledge and perspectives related to concussions and hits to the head in youth football. This survey will take about 10 minutes to complete. Your part in this study is anonymous. This means that no one will know if you took part in this study and no one, including the researcher, will know what your answers are. Any reports or publications based on this research will only use group data and will not identify you or any individual as being part of this study. If you have any questions, please contact [name] ([contact], [contact]). Completion of this survey indicates that you consent to participate.

Football and Sport History (4-13 questions)

Are you a parent, coach or league official? Parent; Coach; League Official [check boxes]

```
[If Coach]
   What level of play do you currently coach? (select all that apply)
   Tine Mite Mighty Mite 10U Jr Pee Wee 12U Pee Wee
                                                                13U Jr Midget 14U High
   School Collegiate Semi-Professional Professional Other
Do your children/child participate in football?
Yes No
   [If yes]
   What level of play do your children/child play? (select all that apply)
   Tine Mite Mighty Mite 10U Jr Pee Wee 12U Pee Wee 13U Jr Midget 14U High
   School Collegiate Semi-Professional Professional Other
                                                                Not Sure
   [If yes]
   Do your children/child participate in the Piedmont Youth Football and Cheer League (PYFCL)? Yes
   No Not Sure
   [If yes]
   What position(s) do your child/children participate in? (select all that apply)
   Center Offensive guard Offensive tackle Quarterback Running back
                                                                          Wide receiver
   Tight end Defensive tackle Defensive end Middle linebacker Outside linebacker Defensive
   back Special teams Other:
   [If yes]
   Has your child ever been diagnosed with a concussion?
   Yes No Not Sure
   [If yes]
   Has your child ever been diagnosed with a concussion while participating in football activities?
   Yes No Not Sure
Have you ever played tackle football?
```

Yes No

[If yes]

What levels of play have you participated in? (select all that apply)

Youth High School Collegiate Semi-Professional Professional Other

[If yes]

What age did you start playing football?

<5 years old 5-10 years old 11-13 years old 14-18 years old >18 years old

[If yes]

Have you ever been diagnosed with a concussion?

Yes No Not Sure

[Yes]

Do you feel you have any lasting effects from your concussion(s)?

Yes No Not sure

Knowledge and Beliefs (10 questions)

Directions: These statements about concussions may or may not be true. Please rate how strongly you agree with each statement.

People who have had a concussion are more likely to have another concussion. Strongly Disagree, Disagree, Somewhat Disagree, Neither Agree nor Disagree, Somewhat Agree, Agree, Strongly Agree

A concussion cannot cause brain damage unless the person has been knocked out. Strongly Disagree, Disagree, Somewhat Disagree, Neither Agree nor Disagree, Somewhat Agree, Agree, Strongly Agree

A concussion can only occur if there is a direct hit to the head.

Strongly Disagree, Disagree, Somewhat Disagree, Neither Agree nor Disagree, Somewhat Agree, Agree, Strongly Agree

Hits to the head that do not result in concussion may affect brain health after one season. Strongly Disagree, Disagree, Somewhat Disagree, Neither Agree nor Disagree, Somewhat Agree, Agree, Strongly Agree

Hits to the head that do not result in concussion may affect brain health later in life. Strongly Disagree, Disagree, Somewhat Disagree, Neither Agree nor Disagree, Somewhat Agree, Agree, Strongly Agree

Do you feel that efforts should be taken to reduce concussions in football? Definitely yes Probably yes Not sure Probably not Definitely not

Do you feel that hits to the head that do not result in concussion should be avoided in football? Definitely yes Probably yes Not sure Probably not Definitely not

Do you think there should be limits on the amount of contact allowed in football practices? Definitely yes Probably yes Not sure Probably not Definitely not

Protocol version:

Template updated 9.24.14

Do you think there should be limits on tackling drills allowed in football practices? Definitely yes Probably yes Not sure Probably not Definitely not

In your opinion, what is the greatest opportunity to reduce hits to the head in youth football?

- a) Limitations on contact in practice
- b) Limitations on drills allowed in practice
- c) Workshops for athletes to teach proper technique
- d) Workshops for coaches to learn safe practices in sport
- e) Rule changes in games
- f) Safer helmets/equipment
- g) Reducing equipment worn by athletes (e.g., removing helmet during practice)
- h) Changing the culture around hits in football (e.g., discouraging celebration of big hits)
- i) No improvements are needed
- *j)* Other, specify:

Which of the following will be the easiest to put in place?

- a) Limitations on contact in practice
- b) Limitations on drills allowed in practice
- c) Workshops for athletes to teach proper technique
- d) Workshops for coaches to learn safe practices in sport
- e) Rule changes in games
- f) Safer helmets/equipment
- g) Reducing equipment worn by athletes (e.g., removing helmet during practice)
- h) Changing the culture around hits in football (e.g., discouraging celebration of big hits)
- i) No improvements are needed
- *j)* Other, specify:

Perceived Susceptibility (5 questions)

Do you think children have more hits to the head while playing football compared to other contact sports (e.g., lacrosse, soccer)?

Much more Slightly more About the same Slightly less Much less

Do you think children have more hits to the head while playing football compared to non-contact sports (e.g., swimming, tennis)?

Much more Slightly more About the same Slightly less Much less

What position do you think has the greatest number of hits to the head in football?

Center Offensive guard Offensive tackle Quarterback Running back Wide receiver Tight end Defensive tackle Defensive end Middle linebacker Outside linebacker Defensive back Special teams Other Equal risk across positions

What position do you think receives the hardest hits to the head in football?

Center Offensive guard Offensive tackle Quarterback Running back Wide receiver Tight end Defensive tackle Defensive end Middle linebacker Outside linebacker Defensive back Special teams Other Equal risk across positions

Protocol version:

Do you think children playing football make contact with their helmet (i.e., receive hits to the head) more often during games compared to practices?

Much more Slightly more About the same Slightly less Much less

Perceived Severity (5 questions)

How serious do you think it is for...

your child/children to have a concussion in football?

Not serious at all Somewhat serious Serious Very serious Extremely serious

your child/children to receive a hard hit to the head in football practices?

Not serious at all Somewhat serious Serious Very serious Extremely serious

your child/children receive a hard hit to the head in football games?

Not serious at all Somewhat serious Serious Very serious Extremely serious

How many hits to the head (making contact with his/her helmet) during a single practice or game would cause you concern?

Less than 5 impacts 6-15 16-25 26-50 Greater than 50 head impacts I am not concerned about the number of head impacts Unknown

If your child/children had a concussion in football, would you be concerned about any of the following outcomes:

Missing one or more practice	Yes	No
Missing one or more games.	Yes	No
Missing one or more days of school.	Yes	No
Decreased performance at school.	Yes	No
Decreased performance in football.	Yes	No
Persistent symptoms following concussion.	Yes	No
Increased risk of second concussion.	Yes	No
Short-term (i.e., single season) effects on brain health.	Yes	No
Long-term (i.e., later in life) effects on brain health.	Yes	No
Other:		

Perceived Needs/Barriers (6-8 questions)

Having a competitive team is more important than reducing hits to the head in football practices. Strongly Disagree Disagree Neither Agree nor Disagree Agree Strongly Agree.

Football teams need to reduce hits to the head in practices.

Strongly Disagree Disagree Neither Agree nor Disagree Agree Strongly Agree.

It will be costly to reduce hits to the head in football practices.

Strongly Disagree Disagree Neither Agree nor Disagree Agree Strongly Agree.

Reducing hits to the head in football practices will help teams win games.

Strongly Disagree Disagree Neither Agree nor Disagree Agree Strongly Agree.

Coaches will be willing to change their practice structure to reduce hits to the head.

Protocol version:

Strongly Disagree Disagree Neither Agree nor Disagree Agree Strongly Agree.

League officials will be willing to put policies into place to reduce hits to the head. Strongly Disagree Disagree Neither Agree nor Disagree Agree Strongly Agree.

Please provide any additional comment on needs within the football community to create safer practices.

Please provide any additional comment on barriers within the football community to creating safer practices.

Self-Efficacy (3 questions)

My youth football league will be able to reduce hits to the head in practices.

Strongly Disagree Disagree Neither Agree nor Disagree Agree Strongly Agree.

My youth football league is willing to commit to reducing hits to the head in practices. Strongly Disagree Disagree Neither Agree nor Disagree Agree Strongly Agree.

My youth football league has the ability to maintain efforts to reduce hits to the head in practices. Strongly Disagree Disagree Neither Agree nor Disagree Agree Strongly Agree.

Demographic (4 questions)

What is your age?

Under 18 18-24 25-34 35-44 45-54 55-64 65-74 75-84 85 or older

What is your gender?

Male Female Prefer not to answer

How would you best describe yourself?

American Indian/Alaska Native Asian Black or African American Native Hawaiian or Other Pacific Islander White Other Prefer not to answer

Are you of Hispanic/Latino/Spanish origin?

Yes No Prefer not to answer

Practice Survey for Coaches

The purpose of this survey is to understand how often specific drills are included in your practices and the perceived frequency and magnitude of hits experienced in five common youth football drills. This survey will take about 8 minutes to complete. If you have any questions, please contact [name] ([contact], [contact]).

1. What is your age? Under 18 18-24 25-34 35-44 45-54 55-64 65-74 75-84 85 or older

2. Do you have a child/children who currently participates in youth football? *Yes No*

3a. [If yes] Do you have a child/children who currently participates in the Piedmont Youth Football and Cheer League (PYFCL)? Yes No Not Sure

3. What level of play do you currently coach? (select all that apply)

Tiny Mite Mighty Mite 10U Jr Pee Wee 12U Pee Wee 13U Jr Midget 14U Other,

Specify:

4. What other levels of play have you previously coached? (select all that apply)

Tiny Mite Mighty Mite 10U Jr Pee Wee 12U Pee Wee 13U Jr Midget 14U

High School Collegiate Professional Other Not Sure None

5. How many years have you coached football (any level)?

0-first year coaching 1-2 3-5 6-10 11-20 More than 20 years

6. How many years have you coached **youth** football?

0-first year coaching 1-2 3-5 6-10 11-20 More than 20 years

7. How many years have you personally played football (any level)? 0 1-2 3-5 6-10 11-20 More than 20 years

8. What levels of football have you personally played?

Youth High School Collegiate Semi-Professional Professional

PRACTICES

9. How many days/week does your team have full contact (i.e., full-speed drills, tackling to the ground) practice?

0 1 2 3 4 5 6 7

10. Do wins/losses affect your practice structure (i.e., what drills are conducted and when) the following week?

- a) Always
- b) Most of the time
- c) About half of the time
- d) Sometimes
- e) Never

Protocol version:

11. H	How often do	you include tl	ne followin	ng drills in your p	ractice structure?	
Every pro	ntra-team scr actice never do this	Most practi		~ .	gies in a game-like situation A few practices	ı
					, & ball carrier; Simulate gar	me speed
	actice never do this		ces	Some practices	A few practices	
	one: 1 vs 1 ta		ith the 2 at	thletes starting less	s than 3 yards apart; Improv	re one-on-one
Every pro	actice never do this	Most practi	ces	Some practices	A few practices	
		l vs 1 tackling ıll-speed gam			rting more than 3 yards apar	rt; Improve
Every pro		Most practi		Some practices	A few practices	
	skill work: A		ate into of	fense & defense g	roups; practice offensive- or	defensive-
Ēvery pro	actice never do this	Most practi	ces	Some practices	A few practices	
Every pro		ig, legwork, p Most practi drill		~	A few practices	
	a) <. b) 6- c) 11	ow many time od) during a fustimes per pr 10 times per pr 1-20 times per tore than 20 ti	all contact actice practice practice	practice?	es contact with their helmet	(i.e., receives
	a hit to the head a) < . b) 6- c) 11		nud (i.e., lo actice practice practice	ow or half-speed d	es contact with their helmet rills, no tackling to the grou	
				ontact and 6 being s experienced in e	g the hardest hit an athlete mach drill?	nay receive in
Install: 0	_	3 4	5	6		
Oklahon 0 1		3 4	5	6		
	version: e updated 9.	24.14		32		

One-on	-one·										
0	1 2	,	3	4	5	6					
· ·	1 2	•	3	,		O					
Open-f	ield tackl	ing:									
0	1 2	_	3	4	5	6					
Position	n skill wo	rk:									
0	1 2	?	3	4	5	6					
15.		•					ften a player	r makes co	ntact with	their helme	et (i.e.,
	receives					?					
				techniqu							
		-		drills/str	ucture (of practio	ce				
				osition							
	G			l/or coacl							
					ior/wan	ting to e	ngage in co	ontact			
	f) O i	ther, sp	ecify:							
1.6	XX7 11	1	. ,	. 1 . 1	. ,	1 1 1	1 411	, 1		1.4 . 1 1	. (*
16.						now nard	d your athle	tes make c	ontact wit	n their heim	iet (i.e.,
	receive h				ctice?						
		-	ery inte								
		-	tereste		,						
				nterestea							
	G	l) No	ot inter	ested at a	all						
17	Would v	ou be	interes	sted in kn	owing l	how ofter	n your athle	etes make (contact wi	th their helr	net (i e
1/.	receive h				_	now one	n your aunc	cies make v	comact wi	tii tiicii iicii	1101 (1.0.,
			ery inte		ctice.						
			tereste								
		/		nterested	1						
				ested at a							
	u	1) 110	Ji iiiiEi	esieu ui i	ııı						
18	What do	vou f	hink is	the great	est onn	ortunity	for improvi	ing head in	nnact safet	ty in youth	football?
10.				ons on co			_	ing nead in	прист вите	ty in youth	iootouii.
	l	/		ns on coi ons on dri		1					
						_	raenee roper techn	າ່າຕາເອ			
							afe practice				
		-		nges in g		s icarri sc	aje praenee	es in sport			
		-		ovements		oded					
			ther, sp		are nec	Jucu					
	9	, 0	iner, sp	recijy.							
19	Head im	nact s	ensors	measure	how ha	rd and h	ow often atl	hletes hit t	heir head i	in sports. V	Vould
1).	-						informed by			_	, Juiu
			ery inte		a pract	ree Plan	inioninou o	, 11000 1111p	5011501	auu.	
			tereste								
		/		nterestea	1						
				rested at a							
	U	7 110	· · · · · · · · · · · · · · · · · · ·	Love and							

Organizational Readiness for Implementing Change (ORIC) – youth football

[League officials or Coaches] are committed to making football practices safe.

[League officials or Coaches] are determined to make football practices safe.

[League officials or Coaches] are motivated to make football practices safe.

[League officials or Coaches] want to make football practices safe.

[League officials or Coaches] feel confident that they can keep the momentum going in making football practices safe.

[League officials or Coaches] feel confident that they can manage the politics of making football practices safe.

[League officials or Coaches] feel confident that the youth football organization can get people invested in making football practices safe.

[League officials or Coaches] feel confident that they can coordinate tasks so that efforts to make football practices safe goes smoothly.

[League officials or Coaches] feel confident that they can keep track of progress in efforts to make football practices safe.

[League officials or Coaches] feel confident that they can handle the challenges that might arise in making football practices safe.

Adult participants will complete an 8-item scale on the acceptability and feasibility of creating a safer practice structure using the validated Acceptability of Intervention Measure (AIM) and Feasibility of Intervention Measure (FIM).⁸⁸

Football Tackle Technique Survey

We would like to invite you to take part in a research project. The purpose of this research is to understand the knowledge and perspectives related to tackling techniques and hits to the head in football. This survey will take between 5 to 10 minutes to complete. Your part in this study is anonymous. This means that no one will know if you took part in this study and no one, including the researcher, will know what your answers are. Any reports or publications based on this research will only use group data and will not identify you or any individual as being part of this study. If you have any questions, please contact [name] ([contact], [contact]). Completion of this survey indicates that you consent to participate.

- 1. What level of play do you currently coach? (select all that apply)
 - a) Youth Tackle
 - b) Youth Flag
 - c) High School
 - d) Collegiate
 - e) Semi-Professional
 - f) Professional
 - g) None
 - h) Other
- 2. What other levels of play have you previously coached? (select all that apply)
 - a) Youth Tackle
 - b) Youth Flag
 - c) High School
 - d) Collegiate
 - e) Semi-Professional
 - f) Professional
 - g) None
 - h) Other
- 3. How many years have you coached football (any level)?
 - a) 0
 - b) 1-2
 - c) 3-5
 - d) 6-10
 - e) 11-20
 - f) More than 20 years
- 4. What levels of football have you personally played?
 - a) Youth Tackle
 - b) Youth Flag
 - c) High School
 - d) Collegiate
 - e) Semi-Professional
 - f) Professional
 - g) None
 - h) Other
- 5. How many years have you personally played football (any level)?

Protocol version:

- *a*) 0
- *b*) 1-2
- c) 3-5
- d) 6-10
- e) 11-20
- f) More than 20 years
- 6. During your football career, what method of teaching tackling technique were you taught as a player? Please describe the method in the free text box below.
 - *a) Free text box*
- 7. What method of teaching tackling technique is currently used by your coaches to teach proper tackling technique? Please select all that apply.
 - a. Heads-Up Football/CoachUp
 - b. Rugby-Style Tackling/Hawk Tackling
 - c. Shoulder Tackling System
 - *d. Other free text box*
 - e. Unknown
 - f. None
- 8. Have you completed any formal training (eg. Webinar, in-person training, etc.) in the methods of tackling technique that you currently use?
 - a) Yes
 - b) No
 - c) Unsure
- 9. How many years have you and your coaches used this method of teaching tackling technique?
 - a) Less than 1 year
 - b) Between 1 and 2 years
 - c) Between 3 and 4 years
 - d) More than 4 years
- 10. Which phrases do your coaches use to teach tackling techniques in games and practices? Please select up to five phrases used by your staff most often.
 - a) Eyes on the Hip
 - b) Break Down
 - c) Chop Your Feet
 - d) Shimmy
 - e) Plant Your Foot
 - f) Head Up
 - g) Eves Up
 - h) Shoulder Across
 - i) Shoulder on the Hip
 - j) Wrap Up
 - k) Facemask on Shoulder
 - l) Hit, Wrap, Drive
 - m) Get Low
 - n) Tackle through the Numbers
 - o) See What You Hit
 - *p) Other free text box*

- 11. Which practice drills do your coaches use to teach and reinforce proper tackling technique in athletes? Please select up to five drills used in your practices most often.
 - a) Open Field Tackling 1 on 1 tackling with greater than 3 yards at start of drill
 - b) Tackle Dummy or Sled Athlete tackles dummy or sled
 - c) I on 1 Tackling I on 1 tackling with less than 3 yards at start of drill
 - *d)* Angle Tackle/Eye Opener Tackling Drill 1 on 1 tackling where athletes approach at an angle
 - e) Shed the Blocker Tackle Drill Linebackers and Defensive Linemen shedding blocks
 - f) Shuffle and Lift Drill/Explosion Lift Drill Half speed drill where tackler practices rolling hips and lifting ball carrier after initial contact
 - g) Wave Drill/Linebacker Hole Drill Tackler must read the hole and tackler ball carrier
 - h) 4 Point Explosion Drill Athletes begin resting knees and explode forward to push opposing athlete
 - i) Other free text box
- 12. If your coaching staff uses film review, what is the purpose of reviewing film with your team? Please select all that apply
 - a) We do not review film
 - b) Review team performance
 - c) Review athlete specific performance
 - d) Review game strategy
 - e) Teach or reinforce technique
 - f) Highlight big plays/hard hits
 - *g)* Other free text box
- 13. How many hours per week does your coaching staff use film to teach and reinforce proper tackling technique in current athletes?
 - *a)* We do not review film for technique
 - b) < 1 hour per week
 - c) 1-2 hours
 - d) 2-3 hours
 - e) 3-4 hours
 - f) > 4 hours
- 14. In your opinion, how effective is your instruction in practice for athletes to use proper technique during games and scrimmages?
 - a) Very effective
 - b) Effective
 - c) Moderately effective
 - d) Slightly effective
 - e) Not effective

Demographic (4 questions)

15. What is your age?

Under 18 18-24 25-34 35-44 45-54 55-64 65-74 75-84 85 or older

16. What is your gender?

